1 INTRODUCTION

1.1 BACKGROUND

Vascular dysfunction in pregnancy, manifesting as pre-eclampsia, fetal growth restriction, and stillbirth, causes significant morbidity and mortality worldwide for mothers and babies. Pre-eclampsia affects up to 6% of pregnancies and causes 500,00 fetal and 70,000 maternal deaths each year(1). Beyond the immediate impacts, mothers who suffer from pre-eclampsia, and children who were growth restricted in utero, have elevated risks of cardiovascular and metabolic disease throughout their lives(2,3).

National guidelines recommend aspirin prophylaxis commenced prior to 16 weeks' gestation to reduce the risk of pre-eclampsia, fetal growth restriction and stillbirth in women at high risk of placental dysfunction(4). The most effective first trimester risk prediction algorithms incorporate uterine artery Doppler measurements and blood biomarkers like placental growth factor (PIGF) or pregnancy associated plasma protein-A (PAPP-A) assessed at 12 weeks' gestation. Despite an ~82% sensitivity for preterm pre-eclampsia, this screening test is a poor predictor for pre-eclampsia occurring at >37 weeks' gestation, which is the majority of disease(5). Moreover, risk stratification tools based on one-off measurements at a single time point cannot predict likely clinical trajectory of disease or time to deterioration. The lack of robust strategies to guide management presents challenges for clinicians, in implementing appropriate prophylaxis, monitoring and timely delivery, and in minimising harms associated with excessive intervention and iatrogenic birth at unduly early gestations.

Ophthalmic artery Doppler indices show promise as predictive markers for pre-eclampsia, at both early and late gestations(6). Meanwhile, retinal microvascular changes are reported preconception, antenatally, and postpartum in women with pregnancies affected by placental dysfunction(7,8,9,10,11). The eye may therefore represent a "window" into maternal cardiovascular adaptation to pregnancy. Serial retinal vascular imaging of pregnant women longitudinally throughout gestation is being carried out through the *I-TEST* study (REC 332944), with the aim of identifying novel retinal imaging-derived biomarkers as non-invasive measures of maternal vascular responses to pregnancy.

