1.2 RATIONALE FOR STUDY

Our main aim is to identify and test novel biomarkers relating to retinal vascular, ophthalmic artery and systemic circulatory blood flows, for early detection of pregnancy complications and integration into models that are predictive of pre-eclampsia, fetal growth restriction and stillbirth. We will use a computational modelling approach to simulate blood flows within the maternal circulation and investigate the relationship between changes in the retinal and uteroplacental circulations during normal pregnancies and those affected by vascular dysfunction. This approach will complement that

of the *I-TEST* study, which aims to develop retinal imaging-derived biomarkers of placental dysfunction and within which our sub-study is nested, by relating structural retinal vascular changes with physiological adaptation of the entire maternal circulation.

We hypothesise that retinal vascular changes reflect the dynamic remodelling of maternal systemic and uteroplacental circulations during pregnancy. This could provide opportunities to monitor vascular responses to pregnancy non-invasively and in real time, allowing improved risk stratification and early detection of pregnancy complications.

To test this hypothesis and achieve our study aims, we will address the following research questions:

- 1. How do retinal blood flows change throughout gestation during uncomplicated and disordered pregnancies, and how do these changes relate to adaptation with maternal systemic and uteroplacental circulations?
- 2. Do resistance patterns within the retinal microcirculation correlate with quantitative metrics derived from retinal vascular imaging?
- 3. Do retinal blood flows correlate with established markers of placental function and clinical pregnancy outcomes?
- 4. Can integrating metrics relating to retinal vascular, ophthalmic artery or systemic circulatory blood flows into predictive models of pre-eclampsia and fetal growth restriction improve their performance, over and above current clinical tools?

We anticipate that biomarkers derived from computational models of the maternal cardiovascular system, as it evolves dynamically throughout gestation, will have utility for serial assessment of pregnant women to monitor their vascular adaptation to pregnancy. This could enable clinicians to manage pregnancies where vascular dysfunction is suspected with a more nuanced, personalised and timepoint-specific approach.

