2.1.2 Secondary Objectives

To integrate the cardiovascular and ultrasound Doppler measurements into personalised computational cardiovascular models that capture changes in vascular resistances and compliances, including within retinal and uteroplacental circulations.

To collect serial urine samples for assessment of proteinuria levels (in addition to blood samples at 36 weeks for measurement of biomarkers of placental dysfunction, and data on key maternal and neonatal outcomes, collected as part of the *I-TEST* study). This will allow correlation of maternal cardiovascular changes with markers of renal microvascular dysfunction, established predictive biomarkers for placental dysfunction, and clinically relevant metrics.

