3 STUDY DESIGN

This is an observational study, designed to characterise the maternal cardiovascular response to pregnancy for subsequent identification of vascular biomarkers of placental dysfunction which are suitable for integration into predictive models. It is nested within the *I-TEST* study, through which participants will undergo serial multimodal retinal imaging between 9 and 39 weeks' gestation.

We propose additional assessments of *I-TEST* study participants, in two sequential study arms:

- a. women recruited in late pregnancy, comprising those with healthy pregnancies (controls) and those with diagnosed pre-eclampsia or fetal growth restriction (cases), studied at fortnightly intervals until birth (phase one); and
- b. women studied longitudinally at approximately 12, 28 and 36 weeks' gestations, and 6 weeks postnatally (phase two). These will be an unselected pregnant cohort, enriched with those at higher risk of placental dysfunction who will be invited to additional study visits in late pregnancy to coincide with appointments for fetal monitoring as clinically indicated.

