6 STUDY ASSESSMENTS

6.1 STUDY ASSESSMENTS

All study visits will take place at the Royal Infirmary of Edinburgh. Where possible, visits will be undertaken to coincide with a routine clinical visit, or with a *I-TEST* study visit for retinal imaging.

The following datasets will be collected at study visits (in addition to data gathered through the *I-TEST* study). In phase one, these will be at fortnightly intervals (±5 days), starting after 34 weeks gestation and continuing until birth. In phase two, these will be at 12, 28 and 36 weeks' gestation and 6 weeks postnatally (±3 weeks for each timepoint), with additional (up to fortnightly) study visits offered for women with diagnosed pre-eclampsia or fetal growth restriction, if these can be aligned with scheduled clinical appointments.

Maternal physiological data:

· Maternal height and weight will be measured.

Maternal cardiovascular data:

- Heart rate and systolic and diastolic blood pressure will be measured lying, sitting and standing.
- Echocardiography or electrocardiography (ECG) cardio-impedance will be conducted for measurement of cardiac output ± aortic size.
- Pulse wave velocity: aortic central pulse wave velocity will be assessed with a tonometry-based device placed sequentially over the carotid and femoral artery in conjunction with simultaneous ECG recording. Peripheral pulse wave velocity will then be assessed with a tonometry-based device placed sequentially over either the carotid and radial arteries, or femoral and popliteal/tibial arteries, in conjunction with simultaneous ECG recording. The distance between points of pulse wave detection will be measured manually to allow calculation of central and peripheral pulse wave velocities. The measurement of pulse wave velocities, both centrally and peripherally, will be repeated three times, or until at least two measures are within 0.5m/s.

Ultrasound assessment:

- Maternal uterine artery Doppler measurements will be made and the pulsatility index from both uterine arteries will be recorded (this assessment is already carried out on all *I-TEST* participants at the 36 week visit *I-TEST-M* would involve further repeated measurements at all study visits).

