9.2 PROPOSED ANALYSES

Participant height and detailed cardiovascular and Doppler ultrasound data collected at study visits will be used to personalise patient-specific cardiovascular models, using a two-tier parameter estimation algorithm within a closed-loop 1D-0D circulatory model of pregnancy as described in Carson et al(13). We will extract outputs from these models including predicted measures of aortic diameter and elasticity, and retinal and placental vascular bed resistances.

We will apply correlation analysis to phase one data, to assess relationships between ophthalmic artery Doppler indices and model-predicted aortic and retinal vascular metrics. This will establish whether individual Doppler indices reflect upstream or downstream vascular properties. We will also assess correlation between ophthalmic artery and uterine artery Doppler indices which might suggest synergy between retinal and uteroplacental circulations. Descriptive statistics will be used to compare measures of ophthalmic artery blood flow and retinal vascular resistances between cases and controls, identifying possible candidate biomarkers.

In phase two, we will use a linear mixed effects regression approach to assess longitudinal changes in vascular metrics within individuals, and identify differences in metric trajectories for pregnancies affected by placental dysfunction. We will validate candidate biomarkers of vascular and placental dysfunction by testing associations with proteinuria and 36-week PIGF levels (from blood samples collected as part of the *I-TEST* study), using linear models adjusted for common co-variates, adjusting for multiple comparisons. Separate subgroup analysis will be performed for participants on antihypertensive treatment.

We will assess the relationship between estimates of retinal vascular resistances generated from computational modelling and structural parameters derived from retinal vascular imaging in the *I-TEST study*, using data from phases one and two. This will be through analysis of correlation between model-prediction retinal vascular resistance and metrics derived at the same gestation from retinal imaging, for individual participants.

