In predictive outcome modelling, we will adhere to PROBAST and TRIPOD guidelines(16,17). For continuous outcomes, such as birthweight, this will be approached as a multivariate linear regression task. For categorical outcomes, including occurrence of specified pregnancy complications, we will apply a logistic regression approach only for sufficiently balanced data. Training/test data splits will be performed using k-fold cross validation. We will evaluate classifiers in terms of precision, recall and area under the receiver-operator curve, and compare these with baselines based on demographic and routine clinical evaluation data.

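### As written, the comparison behind research question 4 can overstate the new biomarkers: its baseline does not name uterine artery Doppler, and selection is not tied to the cross-validation folds

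*Protocol*

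**What the plan says.** Section 1.2, research question 4, asks whether adding retinal, ophthalmic or systemic flow metrics to predictive models can "improve their performance, over and above current clinical tools". Section 1.1 describes the state of the art: "The most effective first trimester risk prediction algorithms incorporate uterine artery Doppler measurements and blood biomarkers like placental growth factor", or PAPP-A, assessed at 12 weeks.

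Section 9.2 sets the comparison. Classifiers are judged on precision, recall and AUC, and the investigators will "compare these with baselines based on demographic and routine clinical evaluation data". On validation it says: "Training/test data splits will be performed using k-fold cross validation". It also commits to PROBAST and TRIPOD.

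The data held are these. Section 6.1: "Maternal uterine artery Doppler measurements will be made and the pulsatility index from both uterine arteries will be recorded", repeated at all study visits. Section 2.1.2 refers to "blood samples at 36 weeks for measurement of biomarkers of placental dysfunction", collected through I-TEST. No 12-week PlGF or PAPP-A is named. Section 9.2 gives the later PlGF a validation role: "testing associations with proteinuria and 36-week PIGF levels".

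On the order of work, phase one (10 cases, 10 controls) suggests candidates (Sections 9.1 and 9.2). Phase two compares metric trajectories between affected and unaffected pregnancies and tests candidates against proteinuria and PlGF (Section 9.2). Integration into prediction models comes after that (Section 2.2.2). Section 3 describes the phase-two women: "These will be an unselected pregnant cohort, enriched with those at higher risk of placental dysfunction".

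**The concern.** Question 4 is about added value, so its answer depends on what the new metrics are added to. Section 9.2 personalises the circulatory models from the cardiovascular and Doppler data taken at visits, which include the uterine arteries, and extracts placental bed resistance among other outputs. If the baseline holds no uterine Doppler, an apparent gain may be a known marker in a new form.

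The second risk is selection. Cross-validation gives an honest estimate only if every step that used the outcome is repeated in each training fold. If biomarkers are chosen by comparing outcome groups in all phase-two women and only then cross-validated in those women, the test folds have already influenced the choice.

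At stake is a positive answer to question 4 produced by a known marker or by chance.

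**Working it through.** The protocol states no AUC, precision or power for the prediction models, so there is no figure to reproduce. Event counts, numbers of candidates, AUCs, correlations, sensitivities and specificities below are assumptions. The protocol supplies only the phase-two size (100 women) and the pre-eclampsia rate (up to 6%).

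**1. Baseline without uterine Doppler.** Let y be the outcome (20% affected). The baseline score is B = noise + 0.74y and uterine Doppler is U = noise + 0.74y, each with AUC Φ(0.74/√2) = 0.70. The new metric is M = ρU + √(1 − ρ²) × noise, so it knows nothing about the outcome beyond U. Logistic models in 100,000 simulated women gave these AUCs:

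| ρ | B | B + M | Gain | B + U | B + U + M | Gain |
|---|---|---|---|---|---|---|
| 0.3 | 0.701 | 0.707 | +0.006 | 0.771 | 0.771 | 0.000 |
| 0.5 | 0.689 | 0.709 | +0.020 | 0.766 | 0.766 | 0.000 |
| 0.7 | 0.700 | 0.742 | +0.042 | 0.774 | 0.774 | 0.000 |

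The proxy's gain exists only when U is left out.

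**2. Selection before the folds.** The setting was 100 women, a baseline score with true AUC 0.70, 10, 20 or 40 pure-noise candidates, the best three by standardised mean difference, 5-fold cross-validation and 400 runs per setting. False gain = AUC(baseline + selected) − AUC(baseline).

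| Events | Candidates | Baseline | Selected on all women | False gain | Selected inside folds |
|---|---|---|---|---|---|
| 6 | 10 | 0.675 | 0.748 | +0.073 | 0.598 |
| 6 | 20 | 0.671 | 0.803 | +0.132 | 0.584 |
| 6 | 40 | 0.674 | 0.833 | +0.159 | 0.553 |
| 10 | 10 | 0.701 | 0.736 | +0.035 | 0.621 |
| 10 | 20 | 0.688 | 0.762 | +0.074 | 0.592 |
| 10 | 40 | 0.697 | 0.803 | +0.106 | 0.600 |
| 20 | 10 | 0.697 | 0.709 | +0.012 | 0.629 |
| 20 | 20 | 0.695 | 0.733 | +0.038 | 0.616 |
| 20 | 40 | 0.703 | 0.766 | +0.063 | 0.619 |
| 30 | 10 | 0.701 | 0.708 | +0.007 | 0.648 |
| 30 | 20 | 0.700 | 0.729 | +0.029 | 0.627 |
| 30 | 40 | 0.705 | 0.751 | +0.046 | 0.627 |

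With selection inside the folds, noise markers lower the AUC in every setting, as they should.

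**3. Precision in an enriched cohort.** Precision = Se·p / [Se·p + (1 − Sp)(1 − p)]. Take specificity 0.90, with sensitivity 0.60 for the new model and 0.40 for the baseline.

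- p = 6%: 0.036/0.130 = 0.277 against 0.024/0.118 = 0.203 (difference 0.074, ratio 1.36).
- p = 20%: 0.12/0.20 = 0.600 against 0.08/0.16 = 0.500 (difference 0.100, ratio 1.20).
- p = 50%: 0.30/0.35 = 0.857 against 0.20/0.25 = 0.800 (difference 0.057, ratio 1.07).

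Both models rise together, and two models with equal sensitivity and specificity differ by 0 at any prevalence.

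**The case against.** Several points against the concern carry weight.

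- **The baseline is undefined, not stated to exclude Doppler.** Routine clinical data could be read to cover it, and Section 1.1 does not say that the best algorithms are the local tools that question 4 means. This stands as a limit on wording. But Section 6.1 presents uterine Doppler as a study or I-TEST measurement, so the natural reading leaves it out. If it was meant to be included, Section 9.2 should say so.
- **PlGF cannot repair every baseline.** It is documented only at 36 weeks, so the 12-week algorithm of Section 1.1 cannot be rebuilt from it. This stands.
- **Leakage is not stated.** Section 9.2 does not place selection outside the folds, phase one supplies candidates from separately recruited women, the PlGF and proteinuria tests do not select directly on the predicted outcome, and PROBAST and TRIPOD are promised. A reader might infer that the comparison will overstate the biomarkers. The text supports only that it can.
- **The largest false gains may never arise.** Logistic regression is reserved for outcomes that are balanced enough. That condition is undefined, but it could rule out 6 to 10 events in 100. Nor should a noise-only model's AUC of about 0.70 be taken as the size of the problem, because question 4 concerns the gain over a baseline.
- **Enrichment does not favour the biomarkers.** A reader might count inflated precision as a third source of bias. It is not, since both models are read in the same women. The absence of calibration from the listed measures is likewise no evidence of a biased comparison, given the reporting commitments.

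**Conclusion.** The point holds in a conditional form: the comparison can overstate the new biomarkers.

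The baseline part is the firmer, because Sections 1.1, 1.2, 6.1 and 9.2 do not fit together. A pure proxy would show a gain of 0.006 to 0.042 AUC for correlations of 0.3 to 0.7 with uterine Doppler, and none once Doppler is in the baseline.

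The selection part is a fair inference from the order of steps in Sections 2.2.2 and 9.2, with k-fold cross-validation the only validation named. If selection precedes the folds, the false gain is about 0.01 to 0.06 AUC with 20 to 30 events and 0.04 to 0.16 with 6 to 10, for 10 to 40 candidates. These sizes rest on assumed counts; the protocol gives none.

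Prediction is part of one secondary endpoint, and the primary endpoint (generating the circulatory models) is untouched. Precision from the enriched cohort does not carry over to unselected pregnancies, but that is a reporting matter, not a bias in the comparison.

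**What to change.** 1. In Section 9.2, define the existing baseline and add a second: clinical data plus uterine artery pulsatility index at the same gestation as the new metrics, with PlGF added for 36-week models only. Make the paired cross-validated AUC difference against this second baseline, with its 95% CI, the answer to question 4.
2. Either lock the candidate list from phase one before any phase-two outcomes are examined, including at the look after the first 50 women (Section 9.1), or repeat all outcome-based selection inside each fold. Split folds by woman, so that repeated visits stay together. If the list is locked from phase one, keep those 20 women out of the evaluation.
3. Report precision with the cohort prevalence beside it, and again at a stated target prevalence, for example the up to 6% for pre-eclampsia in Section 1.1.

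The cost is analysis time, since the data are already to be collected, and reported gains will probably be smaller. Locking from phase one has a further limit: those women are recruited after 34 weeks, so the list may not suit 12- or 28-week models. Selection inside the folds avoids this.

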10 ADVERSE EVENTS

All researchers involved in this study envisage that the extent of adverse events would remain low. All measurements are non-invasive and have been conducted safely in pregnancy without any adverse events. However, in the event of an adverse event, the appropriate investigator will investigate the causality, seriousness and severity. Should any woman be anxious about any of the tests or findings, our experienced team will be available for discussion. The only identified risk is in data security (Table 1).

Table 1: Main risks to data security

Risk description	Security controls	Likelihood	Impact	Risk
Unauthorised access to patient records	NHS Lothian contract of employment. Personnel mandatory training	Low	Medium	Low
Unauthorised access to NHS Lothian servers	Role based and password protected access to NHS Lothian systems with staff working on dedicated NHS Lothian equipment is secure locations	Low	High	Medium
Risk of disclosure of data leaving the NHS Lothian server	Data extracts pseudonymised, disclosure checked before release. SOPs and training according to national guidance	Low	High	Medium
Loss or unauthorised access to data during data transfer between the University of Edinburgh and Swansea University	Data release checked before release. A secure File Transfer Protocol process must be used	Low	Medium	Medium

11 OVERSIGHT ARRANGEMENTS

11.1 INSPECTION OF RECORDS

Investigators and institutions involved in the study will permit study related monitoring and audits on behalf of the Sponsor, REC review, and regulatory inspection(s). In the event of audit or monitoring, the Investigator agrees to allow the representatives of the Sponsor direct access to all study records and source documentation. In the event of regulatory inspection, the Investigator agrees to allow inspectors direct access to all study records and source documentation.

11.2 STUDY MONITORING AND AUDIT

The ACCORD Sponsor Representative will assess the study to determine if a study specific risk assessment is required.

If required, a study specific risk assessment will be performed by representatives of the Sponsor(s), ACCORD monitors and the QA group, in accordance with ACCORD governance and sponsorship SOPs. Input will be sought from the Chief Investigator or designee. The outcomes of the risk assessment will form the basis of the monitoring plans and audit plans.

If considered necessary, ACCORD clinical trial monitors, or designees, will perform monitoring activities in accordance with the study monitoring plan. This will involve on-site visits and remote monitoring activities as necessary. ACCORD QA personnel, or designees, will perform study audits in accordance with the study audit plan. This will involve investigator site audits, study management audits and facility (including 3rd parties) audits as necessary (delete where not required).

12 GOOD CLINICAL PRACTICE

12.1 ETHICAL CONDUCT

The study will be conducted in accordance with the principles of ICH GCP.

Before the study can commence, all necessary approvals will be obtained and any conditions of approvals will be met.

